# **RESEARCH METHODS/PLANS**

Design: Cross-sectional, repeated-measures design.

*Participants:* We will recruit children aged between 7 and 16 years old with a diagnosis of hemiplegia (due to CP or stroke) at Gross Motor Function Classification System (GMFCS) Levels I-III and Manual Ability Classification System (MACS) Levels I-II. We will also recruit a comparison group of age and gender-matched typically developing peers. Inclusion criteria include the ability to read and write English. Children need to be able to see, hear and respond to auditory and visual cues. As such, exclusion criteria are a greater than 10-degree elbow or shoulder flexion contracture in the affected arm, uncorrected visual deficits (e.g., homonymous hemianopsia, oculomotor disturbance, or cortical visual impairment), uncontrolled photosensitive seizures (occurrence of at least one seizure in the last 3 months), hemineglect or cognitive impairments that would prohibit participation (as judged by a parent).

**Recruitment and sites:** The research assistant (RA) will consult the child's electronic medical records and the clinic MD to determine eligibility. They will approach eligible children and families and provide an overview of the study. Children and caregivers will complete informed assent and consent. Recruitment and data collection will take place at Maine Medical Center Pediatric CP clinic (Portland, ME), Spaulding Salem Outpatient Center for Children CP clinic (Salem, MA), and Massachusetts General Hospital Pediatric Stroke clinic (Boston, MA). In addition, we will email the families of the 62 children with CP or stroke in our lab database to invite them to participate in the lab. Typically developing children recruited via emails from our database will also be tested in the ReGame-VR Lab.

**Sample size and power**: We will recruit a convenience sample of 40 children with hemiplegia and 40 typically developing children. This pilot study is designed to obtain estimates of within- and between-child variability for effect size calculations to power a subsequent, more rigorous study design.

*Institutional Research Board Approval:* IRB approval will be obtained from Northeastern University, facilitating a shared and expedited agreement with IRBs of participating sites.

[figure not shown]

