Data management and analysis: We will follow established procedures for eve tracking and kinematic data processing to discard trials in which artifacts are present or children are looking elsewhere and to determine head and hand movement start and end times. RStudio will be used for data analyses. We will check assumptions of normality for parametric analyses; if un-met, non-parametric equivalent tests will be undertaken. Aim 1: Feasibility outcomes will be recorded with counts and proportions. Aim 2: We will calculate the median of the 5 trials for each hand and target location. Of primary interest are estimates of variability as inputs needed for sample size calculations for the subsequent study. Recognizing lack of power, we will undertake inferential statistics for hypothesis generating purposes, including a multiple correlation using Pearson's t-test for each hand and target location. Aim 3: Paired t-tests per hand. Hypothesis-generating analyses for secondary outcomes will compare performance estimates within individuals (touch screen vs HMD-VR, dominant vs non-dominant hand) and between individuals (CP vs typically developing), accounting for age, lesion, and HMD-VR experience. Equipment related: 1) Sanitization: We use Cleanbox VR technology to disinfect VR headsets using UVC light. All peripherals will be sanitized with alcohol wipes and left to dry for a minimum of 15 minutes between users. 2) Transport/set up: Potential difficulties transporting and setting up equipment in different settings can be mitigated by diligent equipment protection. We have transported equipment many times for other studies at the Boston Children's Museum. HMD-VR tracking accuracy is not affected by differing ambient light levels. Study related: 1) Reliability of VMI scoring: The PI (a pediatric physical therapist) will train for VMI scoring by using the VMI manual, attending a web-based presentation on scoring, and scoring practice tests. 2) Lack of experience with eye-tracking processing/analyses: We will consult with [name], Assistant Professor in the College of Science at Northeastern and eye-tracking expert, who will advise on analyses. [name] was unable to be a named investigator on this grant due to budget restrictions. 3) Recruitment: Previous recruitment at Boston Children's Hospital CP clinic (unfortunately not a site for this study due to lack of space for clinic VR assessments) yields 2-3 eligible participants/week for identical inclusion criteria. Estimates from other sites are between 3-10 eligible children per clinic. 4) Time for in-clinic assessment: Recognizing the many demands on children and families' time in a busy clinic

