
environment, we will endeavor to approach families at their arrival and leverage positive relationships with clinic staff to determine the optimal testing time.

Participant related: 1) Previous experience with VR: This may impact performance; this information will be collected in the demographic questionnaire and included as a covariate in the analyses. 2) Potential impact of HMD weight on head or reaching movements: There are no studies of impact of HMD weight on children's movements; the short duration of our testing should mitigate any issue. 3) Left vs right-sided lesion differences in spatial abilities: We will include hemispheric lesion side as a covariate in the analyses, but this is complicated by the fact that many children with unilateral impairments have bilateral lesions. Any hemispheric-specific differences will inform the next study. 4) Intra- and inter-individual variability in this population: Children with hemiplegia are a heterogeneous population and their performance varies across repeated tests within individuals and between children. We will take this into account by basing sample size calculations for subsequent work on effect sizes from this study.

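### Gender is a matching factor for the typically developing group but is missing from the covariates in the between-group comparison; adding it is a small, nearly free improvement.

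*Combined protocol and SAP*

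**What the plan says.** The Participants paragraph (Research Methods/Plans) describes a "comparison group of age and gender-matched typically developing peers". It does not say whether matching is individual or by frequency, and gives no age tolerance. The Sample size and power paragraph adds: "We will recruit a convenience sample of 40 children with hemiplegia and 40 typically developing children".

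The between-group analysis appears in the Data management and analysis paragraph. That sentence opens "Hypothesis-generating analyses for secondary outcomes will compare performance estimates within individuals" and goes on to comparisons "between individuals (CP vs typically developing), accounting for age, lesion, and HMD-VR experience".

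The Participant related paragraph returns to two of these covariates. On previous VR use it says "this information will be collected in the demographic questionnaire and included as a covariate in the analyses". On lesion it says "We will include hemispheric lesion side as a covariate in the analyses". Gender is not named as a covariate in any of these places. The only paired tests in the plan are the Aim 3 t-tests, which compare conditions within a child and not the two groups.

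**The concern.** When a comparison group is built by matching, the matching factors normally go into the analysis as well, either as covariates or through a matched analysis. Here age does and gender does not, and no reason is given.

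Two things could follow. If the achieved gender balance is not exact, any effect of gender on the outcome leaks into the group difference. If it is exact, the variation due to gender stays in the residual. That makes the group comparison slightly less precise and the between-child variance slightly too large. The second matters a little because the pilot's stated purpose is variance estimation: "This pilot study is designed to obtain estimates of within- and between-child variability for effect size calculations".

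**Working it through.** The documents state no power, alpha, SD or gender effect, so there is no figure of the plan's own to reproduce. The first step is textual; the rest is illustration.

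**1. Compare the lists.**
- Matching factors (Participants): age, gender.
- Adjustment factors (Data management and analysis): age, lesion, HMD-VR experience.
- Added under Participant related: nothing new (VR experience and lesion side again).
- Matched on but not adjusted for: gender.

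**2. Standard error of a group difference.** From the documents: 40 children per group. In units of the between-child SD, SE = √(2/40) = 0.22.

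**3. Exact gender balance.** Assumed: gender effect 0.4 SD, 50:50 split.
- Variance explained by gender ≈ 0.25 × 0.4² = 0.04, or 4%.
- SE without gender ÷ SE with gender ≈ 1/√(1 − 0.04) = 1.02, so about 2% too wide.
- Bias: none, because both groups carry the same gender mix.

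Over a range of R², the share of variance explained by gender, the effect on power is as follows. It is taken at the difference that 40 versus 40 detects with 80% power at an assumed two-sided 5% level (0.626 SD).

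| R² for gender | SE ratio | Power with gender added |
|---|---|---|
| 1% | 1.005 | 80.4% |
| 5% | 1.026 | 82.0% |
| 10% | 1.054 | 84.0% |
| 20% | 1.118 | 87.9% |

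A simulation of 3,000 runs per setting, with 60% of one gender in both groups and gender effects of 0.3, 0.5 and 0.8 SD, agrees. Without gender in the model the mean bias was between −0.006 and 0.004 SD and the type I error was 0.045, 0.049 and 0.037. The Monte Carlo error on those rates is √(0.05 × 0.95/3000) = 0.004, so there is no inflation and at most slight conservatism. Power at 0.626 SD was 0.777, 0.765 and 0.744 without gender, and 0.789, 0.787 and 0.798 with it.

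**4. Imperfect gender balance.** Assumed: 60% versus 45% of one gender, a 15-point gap, which is 0.15 × 40 = 6 children.
- Bias without gender = 0.15 × gender effect.
- At 0.4 SD: 0.15 × 0.4 = 0.06 SD. Relative to the SE: 0.06/0.22 = 0.27, about a quarter.
- At 0.3, 0.5 and 0.8 SD: 0.045, 0.075 and 0.12 SD. The simulation gave 0.037, 0.074 and 0.121 without gender, and 0.001, 0.001 and −0.002 with it.

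**The case against.** The best defence is that matching already deals with gender. It has two levels and is easy to balance, and controls can be chosen from the lab database by gender. Age runs continuously from 7 to 16 years and is harder to match closely, so adjusting for age while trusting the match on gender is defensible. If the match succeeds, the estimate is unbiased and the test is, if anything, conservative. This stands, and it limits the size of the point. It does not remove the case for adjusting, because the precision gain remains and no matching procedure is described that would guarantee balance.

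Three stronger readings are tempting, and the documents do not support them.

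- *A reader might infer that the match is probably poor because both groups are convenience samples.* Convenience recruitment does not imply failed gender matching. The documents give no ground for more than the possibility.
- *A reader might infer that ignoring matched pairs makes the standard error 5% to 20% too wide.* That needs a within-pair correlation of 0.1 to 0.3 (1/√0.9 = 1.05; 1/√0.7 = 1.20). Children are matched only on age and gender, and age is already in the model, so the remaining correlation should come mainly from gender. At 0.4 SD that is about 0.04, or 2% on the SE. A correlation of 0.3 from gender alone would need an effect of √(0.3/0.25) ≈ 1.1 SD. One-to-one pairing is not stated either, and the plan names no unpaired test.
- *A reader might infer that a biased group effect will be used to power the next study.* The Participant related paragraph does say that later sample sizes will use effect sizes from this study, but nothing identifies the hemiplegia versus typically developing contrast as the one used. The plan lists that contrast among hypothesis-generating analyses of secondary outcomes.

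It is also fair to say that lesion has no value for typically developing children, so the same model has a separate problem that adding gender does not solve.

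**Conclusion.** The point holds as a minor inconsistency between design and analysis. That gender is matched on but not adjusted for rests on the text alone. The size rests on assumptions: about 2% on the standard error under exact balance with a 0.4 SD gender effect, and a bias of 0.045 to 0.12 SD under a 15-point imbalance with effects of 0.3 to 0.8 SD. Bias arises only if balance is imperfect, which the documents neither show nor rule out.

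The analysis affected is exploratory. On its Aim 2 tests, too, the plan is open about its limits: "Recognizing lack of power, we will undertake inferential statistics for hypothesis generating purposes". The feasibility criteria (Aim 1), the correlations (Aim 2) and the within-child t-tests (Aim 3) are not described as adjusted group contrasts and are not touched. This is worth correcting because it is so cheap, not because a conclusion depends on it.

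**What to change.** In the Data management and analysis paragraph, add gender to the covariates for every comparison of children with hemiplegia and typically developing children.

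Cost: one degree of freedom with 80 children. Gender has to be known in order to match on it, so no new data are needed. Adjustment removes the bias from any leftover imbalance and takes gender variation out of the residual.

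A random effect for matched pair is not required. Once age and gender are both in the model, little pair correlation should remain.

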### **Study Procedures**

## Outcome measures

Aim 1: Feasibility will be determined by achievement of the following:

- a. Recruitment of 40 children with hemiplegia in 24 data collection visits at study sites (average 2/visit: 3 sites, 2 visits/month, 4 months);
- <5% of participants reporting adverse effects (dizziness or motion sickness) during or within 15 minutes post HMD-VR use; and
- c. 90% of participants able to complete the whole protocol in the available clinic timeframe.

**Aim 2:** *2.a.Paper-and-pencil test:* Total score from the Beery-Buktenica VMI test 6th Edition Short form. *2.b. Touchscreen computer and HMD-VR:* Eye-hand proximity, defined as the lag between eye end time and hand end time (i.e. eye movement time – hand movement time), is a gold-standard measure of visual-motor integration that quantifies the coordination of eye and hand movements.

**Aim 3:** Total movement time during the visual-motor integration object transport task in HMD-VR with and without the complex environment.

**Secondary outcomes**. Multiple other temporal and spatial variables related to eye, head and hand movements will be collected for hypothesis-generating purposes. These include reaction time, movement time, amplitude (eye and hand), touch and transport accuracy (hand), peak velocity, sub-movements and trajectory straightness (hand), and spatial position and pitch, yaw and roll orientations.

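### The exploratory hemiplegia v typically developing comparison does not account for test setting, which largely coincides with group

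*Combined protocol and SAP*

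**What the plan says.** Recruitment and sites names three clinics for the children with hemiplegia, beginning: "Recruitment and data collection will take place at Maine Medical Center Pediatric CP clinic". It adds a second route for them: "we will email the families of the 62 children with CP or stroke in our lab database to invite them to participate in the lab". No target or expected uptake is given for that route. For the comparison group, the only route and the only place are these: "Typically developing children recruited via emails from our database will also be tested in the ReGame-VR Lab".

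The sample is fixed by convenience: "We will recruit a convenience sample of 40 children with hemiplegia and 40 typically developing children". The Aim 1a feasibility criterion is "Recruitment of 40 children with hemiplegia in 24 data collection visits at study sites (average 2/visit: 3 sites, 2 visits/month, 4 months", so it places the whole hemiplegia sample at clinic-site visits.

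Matching, described under Participants, is on age and gender. The between-group analysis, under Data management and analysis, is labelled hypothesis-generating for secondary outcomes. It compares performance "between individuals (CP vs typically developing), accounting for age, lesion, and HMD-VR experience". Test setting is not a matching factor, covariate, stratum or sensitivity analysis anywhere in the plan.

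**The concern.** If one group is tested almost entirely in clinics and the other entirely in a laboratory, a difference between the groups could come from hemiplegia, from the place of testing, or from both. Reaction time, movement time and eye-hand timing could plausibly respond to noise, interruption, time pressure or equipment set-up.

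The plan offers one reassurance about measurement conditions across places: "HMD-VR tracking accuracy is not affected by differing ambient light levels". That covers the headset. The touchscreen task uses a different eye tracker and a depth camera, and nothing comparable is said about them. It also does not touch distraction or time pressure.

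At stake is the meaning of the between-group estimates. The pilot exists to inform a larger study, and a group difference taken from it as an effect size would carry any setting effect with it.

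**Working it through.** **1. How many children with hemiplegia are planned in clinics?** Inputs are from Aim 1a: 3 sites, 2 visits a month, 4 months.

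- Visits: 3 × 2 × 4 = 24, which reproduces the plan's figure.
- Children per visit: 40 / 24 = 1.67, which rounds to the stated average of 2.

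The criterion is met in full by clinic visits alone. The clinic share falls to one half only if 20 of the 40 come through the lab database, that is 20 / 62 = 32% of the invited families. So clinics as the main setting is the plan's own target, but the actual split is never stated.

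**2. Bias in the pooled comparison.** The documents give no setting effect, so one must be assumed. Take the outcome in SD units (SD of 1 in both groups), no true group difference, and all typically developing children in the lab. Then

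bias = (share of hemiplegia group tested in clinic) × (setting effect).

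| Clinic share | Setting effect 0.2 SD | 0.3 SD | 0.5 SD |
|---|---|---|---|
| 50% (20 in lab) | 0.10 | 0.15 | 0.25 |
| 75% (10 in lab) | 0.15 | 0.225 | 0.375 |
| 100% (0 in lab) | 0.20 | 0.30 | 0.50 |

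For scale, the standard error of a 40 v 40 difference is √(2/40) = 0.224 SD.

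**3. What can be separated.** No typically developing child is planned in a clinic, so there are at most three cells: hemiplegia in clinic, hemiplegia in lab, typically developing in lab. A setting term can be estimated only from the contrast within the hemiplegia group. Before other covariates enter, adding that term gives the same group estimate as comparing the two lab cells. If the hemiplegia lab cell is empty, no model separates group from setting.

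**4. Precision of the lab-only estimate.** SE = √(1/k + 1/40), where k is the assumed number of lab-tested children with hemiplegia.

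- k = 10: 0.354 SD
- k = 15: 0.303 SD
- k = 20: 0.274 SD

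**5. Bias against precision.** Pooled root mean squared error is √(0.224² + bias²). The lab-only figure is its SE, which generously treats lab attenders as representative.

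| Case | Pooled | Lab-only |
|---|---|---|
| 0.2 SD, 50% clinic | 0.245 | 0.274 |
| 0.3 SD, 75% clinic | 0.317 | 0.354 |
| 0.5 SD, 50% clinic | 0.335 | 0.274 |

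Neither estimate is better throughout, so the lab-only figure belongs beside the pooled one and should not replace it.

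**The case against.** The strongest reply is that the affected analysis is peripheral. Aim 1 is counts and proportions, and Aim 3 is paired tests per hand. Touchscreen v headset and hand v hand are also comparisons within a child. None of these is confounded with setting if each child is tested in one place. The between-group comparison is openly exploratory. This stands, and it limits the point to that one comparison.

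Some handling of clinic conditions is also planned. Trials with artefacts or with the child looking away are discarded, Aim 2 takes the median of 5 trials, equipment is to be protected in transit, and staff will look for a good testing time. Discarding trials removes some of the effect of distraction, but it does not correct slower performance in the trials that are kept. The remarks about busy clinics concern scheduling. A reader might take them as evidence that children perform worse there, but the documents give none.

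A reader might also infer that the group difference will size the next study. The documents do not say so. Sample size and power and the Aim 2 analysis both stress estimates of variability. The closing remark on basing later sample sizes on this study's effect sizes concerns heterogeneity among children with hemiplegia. Use of the group difference is possible, but it is not a documented intention.

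Finally, the biases could be turned into false-positive rates: about 7% to 61% across the bias table, at a two-sided 5% level by normal approximation. The plan sets no alpha and makes no confirmatory test of this difference, so those rates illustrate the assumptions and do not describe the trial.

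**Conclusion.** The point holds for the exploratory between-group comparison and no further. Followed as written, the plan confounds group with setting in part, and completely if Aim 1a is met with no child with hemiplegia tested in the lab. An exploratory label lowers the stakes but does not remove bias.

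The magnitude is unknown. The range of 0.10 to 0.50 SD rests wholly on assumed setting effects and clinic shares. The omission of setting from the analysis is certain; the size of its consequence is not. Nor can one assume that adjustment will rescue the comparison. It depends on enough database children with hemiplegia attending the lab, and those who attend are self-selected, so their contrast with clinic children mixes setting with selection.

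**What to change.** - Record test setting (clinic or lab) for every child.
- Keep the pooled comparison. If enough children with hemiplegia are tested in the lab, report a sensitivity estimate beside it: lab-tested hemiplegia v lab-tested typically developing, or the same model with a setting term.
- Report the clinic v lab difference within the hemiplegia group, noting that lab attendance is self-selected.
- State in the analysis section that the pooled group difference is confounded with setting and must not be used alone as an effect size for the next study.
- If no child with hemiplegia is tested in the lab, state that the two effects cannot be separated.

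The cost is one recorded field and a few sentences in the analysis plan, with no extra children or visits. The drawback is an imprecise sensitivity estimate: a standard error of about 0.35 to 0.27 SD with an assumed 10 to 20 lab-tested children with hemiplegia, against 0.22 SD pooled.

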# Materials and tasks:

**HMD-VR:** We will use the VIVE Pro EYE, the leading commercially-available immersive VR system, which has with a 110 degree trackable field of view and an embedded eye tracker. Arm movements are tracked by lightweight trackers attached via Velcro arm band to children's forearms and ManusVR motion tracking gloves worn on the hands. Head movements are tracked by position sensors in the HMD. Trackers and gloves enable upper extremity interaction with objects in the virtual world (see Figure 2). An Alienware m15 gaming laptop with an NVIDA GeForce RTX 2060 graphics card will run the task. All materials are easily transportable and will be sanitized between users; the HMD-VR will be thoroughly and quickly sanitized using Cleanbox VR.

**Touchscreen computer**: The task will be displayed on a 20" HP Spectre touch-screen laptop with an RTX 960 graphics card. Eye-tracking will be undertaken using a Tobii Eye Tracker 4C which integrates with Unity software. Kinematics of hand movement during reach to touch as well as head movements will be collected using an Orbbec Astra depth-sensing camera. Accuracy of touch is recorded by custom-written software tracking X-Y touch coordinates on the screen. All data collection modalities are synced and integrated using LabVIEW.

**Task programming**: Both 3D and touchscreen tasks will be programmed using the Unity Development Platform, an open-source VR development environment.

